### 4.2 SAR440234

SAR440234 (CD3-CD123 TCE) is a humanized bispecific monoclonal antibody that binds selectively to the human CD123 tumor antigen and CD3 subunit of the T-cell co-receptor.

The structure is composed of a CODV-Fab fragment (CL kappa/CH1) grafted to an Fc IgG1 with LALA mutation to suppress Fc effector function (light chain position 366/367; heavy chain position 358/359). The so-called light chain is composed of 578 amino acids and has a molecular weight of 63 035.52 Da; the heavy chain is composed of 570 amino acids and has a molecular weight of 62800.90 Da.

The structure is illustrated in Figure 1.

Figure 1 - SAR440234 structure

SAR440234 (LC80781, [hz20G6 x hz7G3-N55S with Fc-IgG1-LaLa backbone]) is a novel fully human bispecific antibody TCE molecule that is proposed for the treatment of cancer. The proposed primary indication for SAR440234 CD3-CD123 TCE is AML.

SAR440234 is designed to simultaneously bind CD3, the human T-cell co-receptor molecule, and CD123, the human IL3 receptor alpha chain subunit (IL-3Rα) and thereby co-engage T-cells with CD123-expressing tumor cells, resulting in presentation of tumor cells for T-cell directed tumor-specific killing.

CD123 is aberrantly over-expressed in AML and in other hematological malignancies (MDS, systemic mastocytosis, blastic plasmacytoid dendritic cell neoplasm, B-ALL, and hairy cell leukemia). CD123 is expressed on AML blasts (~80% of positive samples, 63% with more than 80% CD123-positive blasts) and on CD34-positive/CD38-negative AML leukemic stem cells (~90% CD123-positive LSCs) (12). It has little expression outside the hematopoietic system. Thus, CD123 represents an attractive target for therapy in patients with AML.

In vitro studies have shown that SAR440234 induces T-cell activation and cytotoxic activity. Inhibition of AML tumor cell growth was seen with SAR440234 in animal tumor models.

### 4.3 NONCLINICAL TOXICOLOGY

Based on significant sequence homology of human CD3ɛ and CD123 compared to cynomolgus monkey in contrast to rodents, on similar binding affinity to both targets for human and cynomolgus monkey, and on overall similar staining pattern in cross-reactivity studies performed with SAR440234 on human and cynomolgus monkey normal tissues, the cynomolgus monkey was selected as the relevant species for in vivo toxicology evaluation.

Tissue cross-reactivity using normal human and cynomolgus monkey frozen tissues was assessed by immunohistochemistry using SAR440234 conjugated with digoxigenin (SAR440234-DIG). SAR440234-DIG-specific staining was observed in lymphoid tissues, bone marrow and on infiltrating/circulating cells and/or endothelial cells in most tissues in both species demonstrating overall similar staining distribution on human and cynomolgus monkey tissues. The localization of the staining was as expected, based on the reported distribution of CD3 and CD123 antigens.

Consequently, the in vivo gen	neral toxicity studies were conducted	in cynomolgus monkeys, only.
In the repeat-dose monkey st	udies, a progressive weekly intra-mo-	nkey dose escalation was used
in an attempt to mitigate the	cytokine release observed after a sing	gle administration. The doses
used in the 3 conducted monl	key toxicity studies were:	in the single-dose
exploratory study,		in the weekly (x4)
exploratory study and		
(3 males), and	(5 females) in the weekly (	(x6) Good Laboratory Practice
(GLP) study.		
Safety pharmacology endpoin	nts were evaluated in the weekly mor	nkey GLP study. No
SAR440234-related effects w	vere noted on electrocardiogram (ECC	G), blood pressure and
respiration rate in this study u	up to the highest dose tested of	Transient
clinical signs and transient in	creased body temperature noted in th	ne study were considered a
consequence of the cytokines	s release and not a direct effect of SA	R440234 on the central nervous
system.		

The main adverse effects noted in monkeys consisted of marked increases in the levels of cytokines (IL-2, IL-6, IL-10, interferon [IFN] $\gamma$  and/or tumor necrosis factor [TNF] $\alpha$ ) within the 24 hours following compound administration at and above, associated with transient clinical signs (such as raised hair, hunched posture, impaired mobility, subdued/sluggish behavior, lethargy and/or emesis), transient increases in body temperature within the 24 hours following compound administration and transient increases in C-reactive protein (CRP) and ferritin (evaluated in the weekly monkey GLP toxicity study only). These effects resulted in preterminal euthanasia of the monkeys in the single-dose and weekly monkey GLP studies at high doses of 7.5  $\mu$ g/kg and above.

The main target organs identified in the animals that were euthanized at scheduled necropsy consisted of minimally increased cellularity of intravascular neutrophils in the lungs in the single-dose monkey study and minimal to slight increased germinal centers in the spleen in the weekly GLP monkey study.

29-Aug-2019 Version number: 2

In addition, minimal to mild and transient increases in aspartate aminotransferase (AST), alanine aminotransferase (ALT), blood urea nitrogen (BUN), creatinine, bilirubin and/or fibrinogen were noted mainly in the single-dose monkey study.

The local tolerance of SAR440234, evaluated in the weekly monkey GLP study, was good, as no compound-related macroscopic or microscopic findings were noted at the injection sites at any dose level.

Overall, test article-treated monkeys were exposed to SAR440234, with quantifiable plasma concentrations at least at the end of the 1-hour intravenous (IV) infusion (Ceoi). After repeated administration, Ceoi were maintained throughout the different administrations at decreased dramatically at after the fourth administration, most probably due to the presence of anti-drug antibody (ADA, ie, anti-SAR440234 antibody) in the majority of the animals. Consequently, cytokine release mitigation by progressive intra-monkey dose escalation was demonstrated in the weekly monkey exploratory study at the dose of only. It was not possible to conclude on mitigation in the weekly monkey GLP study due to the dramatic decrease in exposure after repeated administration.

Modulation of pharmacodynamic biomarkers in blood and/or bone marrow (depletion of CD123+ cells) was evidenced in the 3 monkey studies from the lowest dose tested and this dose was the no-observed adverse effect level in these 3 monkey studies.

Most of the effects of SAR440234 described above are perfectly in line with the review article on 17 Investigational New Drugs (different CD3 bispecific formats) published by FDA in September 2017: "An FDA oncology analysis of CD3 bispecific constructs and first-in-human dose selection" (15).

# 4.4 PHARMACOKINETICS IN ANIMAL

The nonclinical pharmacokinetics of SAR440234 were investigated in the toxicological species (cynomolgus monkeys) following an IV (1-hour infusion) administration of H-SAR440234 to overcome the limitation of the immunoassay sensitivity. Following a single IV (1 hour) administration to cynomolgus monkeys, the radioactivity exhibited a bi-compartmental pharmacokinetic profile. The volume of distribution ranged from and clearance ranged from . Terminal elimination half-life was around Exposure assessed by area under the curve (AUC) increased slightly less than expected by dose increase, with a increase in AUC for a increase in dose.

As the drug substance is a therapeutic protein, no other evaluation was conducted for absorption, distribution, elimination or excretion. It is generally recognized that antibodies are metabolized by degradation into small peptides and individual amino acids following endogenous catabolism, therefore no metabolism studies were conducted.

### 4.5 STUDY DESIGN RATIONALE

# 4.5.1 Choice of starting dose

The first-in-human (FIH) study is proposed as a single agent trial in patients with R/R AML, HR-MDS, and B-ALL. This trial is intended to establish proof-of-concept for this drug, based on clinical, pharmacokinetic, and biomarker evaluation; to assess the safety and preliminary anti-leukemic activity of SAR440234; and to define the optimal single agent dose for future studies. The FIH Phase 1/2A study will include a Dose Escalation Part to determine the recommended dose, followed by an Expansion Part at the recommended Phase 2 dose (RP2D). SAR440234 falls into the class of potent immunomodulatory agonists, and as recommended by ICHS9 guidances, it is proposed to use a conservative minimal anticipated biological effect level (MABEL) approach to define the starting dose for the FIH study.

The most sensitive and relevant assays using in vitro human material were selected for the MABEL determination. The anti-tumor efficacy of SAR440234 on disseminated human primary AML in vivo in the NSG mouse model was not incorporated in the MABEL determination, as the translational value of this model was uncertain.

In vitro, in a depletion assay using peripheral blood mononuclear cells from human healthy donors, SAR440234 depleted CD123-positive monocytes with a first effective concentration producing 80% effect (EC80) of \_\_\_\_\_\_\_. This activity was associated with a 20% cell depletion.

The MABEL was calculated using the most sensitive data on CD123-positive cell depletion  $(C_{MABEL})$  with pharmacokinetic modeling to determine the FIH dose, according to the equation:  $Dose = C_{MABEL} \times Vc_{human}$ . It is a conservative approach (Duff method, 2006 [16]), assuming the total dose is administered as a bolus and instantly distributed into total plasma volume.

 $V_{Chuman}$ , volume of the central compartment in human, was obtained from pharmacokinetic parameters determined in monkeys from 2-compartment model analysis and scaled to human,

according to the following equation: 
$$Vc_{human} = Vc_{monkey} \times \left(\frac{BW_{human}}{BW_{monkey}}\right)^{\alpha}$$
, with  $BW_{human} = 70 \text{ kg}$ ,

$$BW_{monkey} = 3 \text{ kg and } \alpha = 1 \text{ (17)}$$

$$V_{C_{human}}$$
 was determined as

The FIH dose was determined as  $Dose = mng/mL \times mng/kg = mng/kg$  and the nearest convenient dose was set to 1 ng/kg.

In conclusion, the recommended starting dose for FIH administration is

# 4.5.2 Clinical rationale

The proposed primary indications for SAR440234 are R/R AML, and HR-MDS. As discussed above, CD123 is highly expressed in most AML blasts, on CD3-positive/CD38-negative AML leukemic stem cells, and in B-ALL cells (18). CD123 has little expression outside the hematopoietic system. For these reasons, CD123 is an important therapeutic target in patients with AML and other hematologic malignancies that express CD123.

Because CD123 is expressed in the leukemic blasts from a majority of patients with AML, the selection of patients for CD123-expressing leukemic blasts in the FIH phase 1 is not recommended. Nonetheless, in vitro experiments have demonstrated that CD123 density might influence SAR440234 efficacy (sanofi, unpublished data). Thus, in the clinic, CD123 expression prevalence and cell density will be monitored in leukemic cells, blasts and LSCs, and in normal cells known to express CD123, such as basophils, plasmacytoid dendritic cells, and monocytes. The depth of CD123-positive cell depletion will be utilized as a pharmacodynamic monitoring marker of SAR440234 efficacy.

In the literature, very little has been reported about the T-cell subpopulation presence and state of activation or exhaustion in patients with AML. Because SAR440234's mechanism of action relies on its ability to recruit and activate T-cells, T-cell sub-populations will be monitored in the FIH study. In addition to monitoring CD123-expression and T-cell sub-populations, clinical sites participating in the testing of SAR440234 will be asked to provide data on the cytogenetic profile and molecular alterations observed in the leukemic cells of AML and MDS patients entering the clinical trial, as is now routine in the risk-stratification of AML and MDS patients (19). The sites will be required to obtain and record the results in the clinical database.

# 4.5.3 SAR440234 dose and regimen

A dose escalation single agent trial will be initiated in patients with R/R AML, HR-MDS, and B-ALL. This trial is intended to establish proof-of-concept for this drug, based on clinical, pharmacokinetic, and biomarker evaluation; to assess the safety and preliminary anti-leukemia activity of SAR440234; and to define the optimal dose of drug as a single agent.

Use of intra-patient dose escalation is proposed. This dosage strategy has already demonstrated its benefit in approved drugs, such as Blincyto®, with the same objective of cytokine release syndrome (CRS) mitigation. The strategy of intra-patient dose escalation is currently being used for other drugs under development.

In the first 2 dose levels (DL1 and DL2), SAR440234 will be administrated once weekly. After evaluation of the first 2 dose levels, a 2-step dosing increase in the first week of administration will be implemented to reach higher exposure in a shorter time frame.

A weekly schedule (bi-weekly during Cycle 1, Week 1 in DL  $\geq$ 3) will be evaluated with drug administration on Days 1, 4 (DL  $\geq$ 3 only), 8, 15, 22, 29, and 36 of a 6-week cycle that will be repeated, provided that the patient is achieving clinical benefit.

29-Aug-2019 Version number: 2

Cycles run consecutively so that Day 1 of each cycle is normally 7 days after the start of the last infusion in the previous cycle. If bone marrow hypocellularity Grade 4 or hematological toxicity Grade 3 or 4 is diagnosed, the interval between doses must be extended until toxicity is resolved. If the interval between doses is or exceeds 10 days, the treatment must be restarted with the lead-in doses appropriate for the selected dose level.

Systematic premedication with the corticosteroid, dexamethasone (two doses of 20 mg IV), and leukotriene inhibitor montelukast (one dose of 10 mg by mouth) are planned starting with the first dose of SAR440234 tested. Dexamethasone and/or tocilizumab will be used to treat Grade ≥2 CRS, as described below and in Section 6.7. Dexamethasone has been chosen because it penetrates the blood-brain barrier (20).

Use of intra-patient dose escalation is proposed. This dosage strategy has already demonstrated its benefit in approved drugs, such as Blincyto®, with the same objective of CRS mitigation. The strategy of intra-patient dose escalation is currently being used for other drugs under development, as well.

# 4.5.4 Cytokine release syndrome

Cytokine-associated toxicity, also known as CRS, is a nonantigen specific toxicity that occurs as a result of potent immune activation. It manifests clinically when large numbers of lymphocytes (B-cells, T-cells, and/or natural killer cells) and/or myeloid cells (macrophages, dendritic cells, and monocytes) become activated and release inflammatory cytokines. Cytokine release syndrome has classically been associated with therapeutic monoclonal antibody infusions and in these settings, symptom onset typically occurs within minutes to hours after the infusion begins (21, 22, 23). Cytokine release syndrome has also recently been reported following administration of bispecific antibodies for leukemia, infusion of haploidentical mononuclear cells to patients with refractory leukemia, and adoptive immunotherapies for cancer, most notably T-cells engineered to express chimeric antigen receptors (18, 24, 25, 26, 27).

The timing of symptom onset and CRS severity depends on the inducing agent and the magnitude of immune cell activation. The incidence and severity of the syndrome also appears greater when patients have large tumor burdens, presumably because this leads to higher levels of T-cell activation. As with CRS associated with monoclonal antibody therapy, CRS associated with adoptive T-cell therapies has been associated with elevated IFN-γ, IL-6, and TNFα levels, and increases in IL-2, granulocyte macrophage–colony-stimulating factor (GM-CSF), IL-10, IL-8, IL-5, and fractalkine have also been reported (26, 28). Emerging evidence implicates IL-6 as a central mediator of toxicity in CRS. IL-6 is a pleiotropic cytokine with anti-inflammatory and proinflammatory properties. However, real time analysis of a broad panel of cytokines will not significantly impact management of individual patients with CRS, thus it is recommended that treatment decisions are based on clinical parameters (29).

In this FIH trial, plasma levels of cytokines, including IL-6 and IFN-γ, will be collected, as well as assays for serum CRP and ferritin. Sampling will be performed following the initial dose and after each dose increase, in order to assess for signs of CRS. C-reactive protein is an acute phase reactant produced by the liver, largely in response to IL-6. Serum CRP levels may serve as a surrogate for increases in IL-6 bioactivity (30). During CRS, serum CRP levels may increase by several logs. The serum CRP assay is rapid, inexpensive, and readily available in most hospitals.

In some series, peak CRP levels and fold-change in CRP have identified patients at risk for severe CRS (26). It is important to emphasize, however, that CRP levels are also elevated during infection and cannot be used to distinguish between inflammation caused by infection and inflammation related to CRS. Extreme elevations in serum ferritin have been observed in many patients with CRS after chimeric antigen receptor T-cell infusion, which supports a resemblance between CRS and macrophage activation syndrome/hemophagocytic lymphohistiocytosis.

To assess and record the severity of CRS in individual patients, the National Cancer Institute (NCI) Consensus Guidelines 2014 will be used (29, 31), and the mitigation strategy for CRS (Appendix H), is based on these guidelines. This grading system defines mild, moderate, severe, and life-threatening CRS, regardless of the inciting agent, and provides treatment recommendations with corticosteroids and/or tocilizumab (29). Tocilizumab is a humanized, immunoglobulin (Ig)G1k antihuman IL-6R mAb approved for treatment of rheumatoid arthritis, juvenile idiopathic arthritis, and polyarticular juvenile rheumatoid arthritis (32, 33). Emerging clinical experience at several institutions has demonstrated that tocilizumab is an effective treatment for severe or life-threatening CRS (28). The FDA has approved tocilizumab for the treatment of chimeric antigen receptor T-cell induced severe or life-threatening CRS. The recommended dose of tocilizumab for treatment of CRS is 12 mg/kg IV for patients weighing <30 kg and 8 mg/kg IV for patients weighing ≥30 kg. Doses of tocilizumab should not exceed 800 mg per infusion. It is also recommended that tocilizumab should not be started in patients with an absolute neutrophil count (ANC) <2000/microliter, platelet count <100 000/microliter, or with an ALT or AST >1.5 times the upper limit of normal (ULN).

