### 4.6 BENEFIT RISK ASSESSMENT

Severe CRS is an anticipated risk due to release of cytokines following T-cell activation. Anemia, leukopenia, and thrombocytopenia are other anticipated risks that commonly occur during treatment for hematologic malignancies. The safety monitoring and risk mitigation plan includes the following measures:

- Systematic premedication with dexamethasone and montelukast will be provided starting with the first dose of SAR440234 tested.
- Treatment with tocilizumab will be started if CRS Grade 2 is diagnosed. Two doses of tocilizumab will be available on site for each patient under treatment.
- A conservative MABEL approach is planned to define a very low dose as the starting dose in humans.
- Careful intra-patient dose escalation with conservative increases for each dose level will be performed. The dose escalation cohort will be initiated at a lower dose at the first infusion in each patient. The purpose of this design is to minimize exposure to sub-therapeutic doses while maintaining patient safety, particularly in the context when the FIH starting dose is very low. This strategy will facilitate rapid attainment of active therapeutic doses.
- Extensive clinical monitoring will be conducted during the Dose Escalation Part, including frequent assessment of vital signs during infusion and at specific time points post infusion. During Cycle 1 and the first 2 doses of Cycle 2 in the Dose Escalation Part, patients will

be hospitalized for the duration of each SAR440234 infusion (1 to 19 hours) and for the first 72 hours after the infusion is completed. During Cycle 1 and the first 2 infusions of Cycle 2 in the Expansion Part, patients will be hospitalized for the duration of the SAR440234 infusion (1 to 19 hours), and for 72 hours after completion of each infusion. During the remaining infusions of Cycle 2 and beyond in the Expansion Part, if the patient has tolerated the SAR440234 infusion well, the patient will be hospitalized only for the duration of each subsequent infusion (1 to 19 hours). The 2014 NCI Consensus Guidelines will be used to grade and guide the management of CRS (Appendix H).

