
Table 11 - Evaluation and management of cytokine release syndrome

Grade	Evaluation	Treatment
1	
 
Monitoring at least every 30 minutes:
 
BP, HR, temperature, respiratory rate, oxygen saturation.
 
Symptom assessment.
 
	Symptomatic treatment with acetaminophen and/or antihistamine, if needed
2	As for Grade 1, with addition of the following: Continuous monitoring of: BP. Oxygen saturation. HR. Monitoring at least every 8 hours, or more frequently if needed, of: PaO 2 . ECG. Blood chemistry.	As for Grade 1, with addition of the following:  • Mandatory transfer of the patient to ICU.  • IV fluid resuscitation and institution of vasopressors.  • Supplemental oxygen.  • Start tocilizumab:  - 8 mg/kg IV once for patients weighing ≥30 kg,  - 12 mg/kg IV once for patients weighing <30 kg,  - If insufficient improvement in CRS within 12 hours, repeat tocilizumab at the same dose every 12 hours for a total of 3 doses.
3	As for Grade 2, with the addition of echocardiography if there is concern for cardiac dysfunction.	
 
As for Grade 2, with addition of the following:
 
High-dose or multiple vasopressors Table 12 to treat hypotension or poor perfusion.
 
If no improvement in CRS within 24 hours, start dexamethasone 10 mg IV every 6 hours.
 

4	As for Grade 3.	As for Grade 3, with the addition of mechanical ventilation if required.

BP=blood pressure, CRS=cytokine release syndrome, ECG=electrocardiogram, HR=heart rate, ICU=intensive care unit, IV=intravenous, PaO2=partial pressure of oxygen in arterial blood

NOTE: Grading of CRS is based according to 2014 National Cancer Institute Consensus Guidelines (see Table 10).

For each patient treated, the hospital must have an available bed in the intensive care unit (ICU) in case the patient develops hemodynamic or respiratory compromise. The ICU should be staffed by a critical care physician who has experience in treating CRS. In addition, the ICU must have the necessary equipment to commence immediate treatment and monitoring of a patient with CRS Grade  $\geq$ 2 before he/she is admitted to ICU. Vital signs monitoring shall be made continuously if CRS Grade  $\geq$ 2 develops.

High dose vasopressors are described in Table 12.

Table 12 - High dose vasopressors

Vasopressor	Dose
Norepinephrine monotherapy	≥20 mg/min
Dopamine monotherapy	≥10 mg/kg/min
Phenylephrine monotherapy	≥200 mg/min
Epinephrine monotherapy	≥10 mg/min

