If on vasopressin	Vasopressin + norepinephrine equivalent of ≥10 mg/min
If on combination vasopressors	Norepinephrine equivalent to ≥20 mg/min
(not vasopressin)	

All doses are required for  $\geq$ 3 hours

Property of the Sanofi Group - strictly confidential

Page 67

29-Aug-2019 Version number: 2

Dexamethasone, vasopressors, and oxygen must be tapered quickly after resolution of CRS.

Dexamethasone 20 mg IV must be repeated 5 hours after the start of infusion if CRS Grade 2 has occurred in a previous patient or previous administration in the same patient. This rule will be applied for the same patient who experienced a CRS event for subsequent infusions and for all patients subsequently enrolled at that dose level or higher.

Symptomatic treatment and/or pre-medication may include: diphenhydramine 25 to 50 mg IV (or equivalent), ranitidine 50 mg IV (or equivalent), and acetaminophen 650 to 1000 mg PO 15 to 30 minutes (but no longer than 60 minutes) prior to infusion, or during infusion at the Investigator's discretion.

For patients with CRS Grade ≥2, tocilizumab will be administered at 8 mg/kg infused over 1 hour for patients weighing ≥30 kg (maximum dose 800 mg) or 12 mg/kg infused over 1 hour for patients weighing <30 kg. Another 8 mg/kg or 12 mg/kg dose IV may be administered in patients weighing ≥30 kg (maximum dose 800 mg) or 12 mg/kg for patients weighing <30 kg, respectively, if there is insufficient clinical improvement 12 to 24 hours after the first dose. Up to 3 doses of tocilizumab may be given.

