# 8.2 NONINVESTIGATIONAL MEDICINAL PRODUCT(S)

**Dexamethasone:** 4 mg/mL for IV injection.

**Tocilizumab:** 200 mg/10 mL vial for IV injection.

**Montelukast:** 10 mg tablet for oral administration.

Dexamethasone 20 mg IV will be instituted as systematic premedication 4 hours and 1 hour prior to each initial IMP administration.

Montelukast tablets 10 mg will be given orally once, 4 hours before the start of SAR440234 infusion.

Dexamethasone 20 mg IV must be repeated 5 hours after the start of infusion if CRS Grade 2 has occurred in a previous patient or previous administration in the same patient. This rule will be applied for the same patient who experiences a CRS event for subsequent infusions and for all patients subsequently enrolled at that dose level or higher.

29-Aug-2019 Version number: 2

For each patient treated, the clinical site must have at least 2 full doses of tocilizumab in the clinical pharmacy ready for immediate administration in case of CRS Grade 2 or above. Guidelines for management of patients with CRS are included in Section 6.7.

For patients with Grade 2 CRS, tocilizumab will be administered at 8 mg/kg infused over 1 hour for patients weighing ≥30 kg (maximum dose 800 mg) or 12 mg/kg infused over 1 hour for patients weighing <30 kg.

If there is insufficient improvement in CRS within 12 hours, tocilizumab may be repeated at the same dose every 12 hours for a total of 3 doses. The interval between consecutive doses should be at least 8 hours. Subcutaneous infusion of tocilizumab is not approved for CRS treatment. Tocilizumab must not be used for prophylaxis of CRS. Patients with Grade 3 or Grade 4 CRS should be treated with tocilizumab as for patients with Grade 2 CRS. For patients with Grade 3 or Grade 4 CRS who do not respond to tocilizumab within 24 hours, dexamethasone 10 mg IV should be given every 6 hours.

For patients weighing ≥30 kg or more, tocilizumab should be diluted in 100 mL of 0.9% or 0.45% sodium chloride injection USP for IV infusion and administered by drip infusion over 1 hour. For patients weighing <30 kg, tocilizumab should be diluted in 50 mL of 0.9% or 0.45% sodium chloride USP for IV infusion and administered by drip infusion over 1 hour. Tocilizumab should not be given as a bolus or push.

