# Appendix H Grading System and mitigation strategy for CRS, based on 2014 NCI Consensus guidelines

Grade	Toxicity	Intervention
Grade 1	Fever, nausea, fatigue, headache, myalgias, malaise, without life-threatening complications.	
 
Vigilant supportive care.
 
Assess and treat infection if present.
 
Fluid resuscitation.
 
Provide antipyretics and analgesics, if needed.
 

Grade 2	
 
Oxygen requirement <40% FIO2.
 
Hypotension responsive to low-dose or single vasopressor.
 
Grade 2 organ toxicity
 
	
 
As for Grade 1, but monitor cardiac and other organ function closely.
 
Consider corticosteroids and/or anti-IL6 therapy for patients with advanced age or multiple co-morbidities.
 

Grade 3	
 
Oxygen requirement >40% FIO2.
 
Hypotension responsive to high-dose or multiple vasopressors.
 
Grade 3 organ toxicity.
 
Grade 4 increase in ALT or AST.
 
	As for Grade 2, but with the addition of corticosteroids and/or anti-IL6 therapy.
Grade 4	
 
Life-threatening symptoms.
 
Requirement for mechanical ventilation.
 
Grade 4 organ toxicity, excluding increase in ALT or AST.
 
	As for Grade 2, but with the addition of corticosteroids and/or anti-IL6 therapy.
Grade 5	Death	

Grading system based on the 2014 NCI Consensus Guidelines (29, 31).

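### Section 4.5.4 advises against starting tocilizumab in patients with low counts or raised transaminases, with no exception for CRS, while the treatment sections direct it for CRS Grade 2 or higher and never mention those limits

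*Protocol*

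**What the plan says.** Protocol section 4.5.4, headed Cytokine release syndrome, gives the weight-based tocilizumab dose for CRS and its cap. The next sentence recommends that "tocilizumab should not be started in patients with an absolute neutrophil count (ANC) <2000/microliter, platelet count <100 000/microliter", and adds ALT or AST above 1.5 x ULN as a third limit. Nothing there says whether the limits hold when the drug is given for CRS.

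The sections that direct treatment read differently:

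- Section 4.6: "Treatment with tocilizumab will be started if CRS Grade 2 is diagnosed".
- Section 6.7.1: "For patients with CRS Grade ≥2, tocilizumab will be administered at 8 mg/kg infused over 1 hour" (the dose for patients of 30 kg or more). Table 11 in the same section lists tocilizumab at Grade 2, and its Grade 3 and 4 rows build on that list.
- Section 8.2 and the synopsis direct it for Grade 2, and for Grades 3 and 4 in the same way.

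None of these repeats, cross-refers to or waives the limits.

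Two places are looser. Section 4.5.3 says "Dexamethasone and/or tocilizumab will be used to treat Grade ≥2 CRS". Appendix H asks only that corticosteroids or anti-IL6 therapy be considered for some patients at Grade 2, and at Grades 3 and 4 reads "As for Grade 2, but with the addition of corticosteroids and/or anti-IL6 therapy". Neither mentions counts or liver tests. The SAP contains no CRS treatment rules.

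**The concern.** Severe CRS is the first anticipated risk named in section 4.6, and tocilizumab is one of the mitigation measures listed there. The same section says: "Anemia, leukopenia, and thrombocytopenia are other anticipated risks that commonly occur during treatment for hematologic malignancies". So the patients most exposed to the main risk of the drug are also patients likely to have counts below the 4.5.4 limits. If an investigator takes 4.5.4 at its word, a patient with Grade 2 or higher CRS and low neutrophils, low platelets or raised transaminases does not receive the treatment that 6.7.1 orders. Two sites could manage the same event differently, each with a protocol sentence in support.

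**Working it through.** There is no stated figure to reproduce. The check is whether the limits and the treatment orders can apply to the same patient, and whether any text settles which prevails.

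**Step 1: can an eligible patient be under the limits at entry?**

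| Parameter | 4.5.4: do not start | Eligibility (7.3, E 03) | Eligible but under the limit |
|---|---|---|---|
| ANC | below 2000/microliter | no minimum | below 2000/microliter |
| Platelets | below 100 000/microliter | no minimum | below 100 000/microliter |
| ALT or AST | above 1.5 x ULN | excluded above 2.5 x ULN | above 1.5 and up to 2.5 x ULN |

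E 03 does exclude certain Grade 4 conditions, among them febrile neutropenia, marrow hypocellularity and life-threatening thrombotic thrombocytopenic purpura. None of these is a floor on ANC or platelets. The DLT definitions in 6.2.1 qualify Grade 4 neutropenia and Grade 4 thrombocytopenia by whether they were present at baseline, so such patients are expected. The pre-infusion blood check in 6.7.1 refers back to the same eligibility criteria and does not screen them out.

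**Step 2: can CRS itself put a patient over a limit?** Table 10 and Appendix H both list Grade 4 transaminase elevation among the criteria for Grade 3 CRS. Assuming that Grade 4 lies above 1.5 x ULN (the protocol does not print the CTCAE cut-offs), a patient graded on that criterion is directed to tocilizumab by Table 11 and advised against it by 4.5.4.

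**Step 3: does any text settle the matter?**

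- Section 6.7.1 says that CRS is managed according to Table 11, but does not set 4.5.4 aside.
- Section 4.5.3 sends the reader both to the text below it, which is 4.5.4, and to section 6.7.
- Section 4.6 says that the guidelines in Appendix H will guide CRS management, and section 17 makes the appendices part of the protocol.
- E 12 excludes known contraindications to tocilizumab. It does not name these limits and cannot cover values that change on treatment. If it did include them, it would exclude patients whom 6.2.1 foresees enrolling.

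**Result.** The two instructions overlap on all three parameters, and no sentence says which one holds in CRS.

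**The case against.** The strongest reply is that the order of authority is clear enough. The limits appear once, worded as a recommendation, at the end of a paragraph in the introduction and rationale. The operative section is 6.7.1, and sections 8.2, 8.6 and 10.2 also point to section 6.7. Sites are chosen for CRS experience, and the ICU should have a physician experienced in treating it. That a site would actually withhold tocilizumab is conjecture. This stands as a reason to expect few errors. It does not remove the conflict: the limits directly follow the CRS dose, 4.5.3 points to that text as well as to 6.7, and training does not decide which instruction is the compliant one.

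A reader might infer more, in two ways that the documents do not support.

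The first is that the steroid rules for Grade 3 and 4 CRS also conflict. Table 11 says "If no improvement in CRS within 24 hours, start dexamethasone 10 mg IV every 6 hours", while 8.2 and the synopsis address patients "who do not respond to tocilizumab within 24 hours, dexamethasone 10 mg IV should be given every 6 hours". But the Grade 3 row of Table 11 adds to the Grade 2 list, which already includes tocilizumab. Read as written, the three places agree: tocilizumab first, then dexamethasone if there is no improvement at 24 hours. Appendix H gives no timing, so it cannot be read as requiring an immediate start.

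The second is that steroid timing could change DLT counts. Grade 3 or 4 CRS is a DLT under 6.2.1 whatever treatment is given. Grade 2 CRS counts as a DLT if it lasts more than 48 hours or is present less than 48 hours before the next dose, so withholding tocilizumab might matter there. The documents give nothing with which to show or size such an effect.

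**Conclusion.** The inconsistency is real and should be corrected. It is confined to one point: whether the ANC, platelet and transaminase limits in 4.5.4 apply when tocilizumab is given for CRS. Its reach, in terms of the documents, is any eligible patient with ANC below 2000/microliter, platelets below 100 000/microliter or ALT/AST above 1.5 x ULN, whether at entry or later. How many patients that is cannot be stated without baseline counts and a CRS rate. The conclusion rests on the wording alone; the only assumption, used in step 2, is that Grade 4 transaminase elevation lies beyond the 1.5 x ULN limit.

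This is a matter of patient safety and of consistent instructions to sites. It does not touch the Simon design, the analysis populations or any statistical figure. The SAP (4.3, 4.4 and 4.9) records early termination, which limits the practical effect in this trial but does not make the text consistent.

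**What to change.** In section 4.5.4, delete the ANC, platelet and ALT/AST limits, or state that they do not apply to tocilizumab given for CRS. In the same place, state that Table 11 governs CRS treatment wherever 4.5.3, 4.5.4 or Appendix H differs from it. That one sentence also deals with the looser wording in 4.5.3 and Appendix H. No new steroid rule is needed: once the limits are removed or waived for CRS, the stated reason for withholding tocilizumab is gone, and an added rule would be a separate clinical decision.

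The cost is a short wording change by amendment and a notice to sites, with no change to sample size, schedule or data collection. Given the early termination, the correction matters mainly for any patient still on treatment and for any later protocol that reuses this text.
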